**Figure 1. Interpretation and Management of HBV Serologic Test Results**

DNA = deoxyribonucleic acid; HBs Ag = hepatitis B surface antigen; HBc Ab = hepatitis B core antibody; HBV = hepatitis B virus; PCR = polymerase chain reaction

\* A positive test result for HBs Ab is expected for subjects who have had a HBV vaccination. For subjects without a history of HBV vaccination (and where mandated by local requirements), a positive result for HBs Ab requires HBV DNA PCR testing.

### HIV Testing

HIV testing will be performed at Screening. The investigator must discuss any local reporting requirements to local health agencies with the subject. The site will report confirmed positive results to their health agency per local regulations, if necessary. If a subject has a confirmed positive result, the investigator must discuss with the subject the potential implications to the subject's health and subject should receive or be referred for clinical care promptly. A subject will not be eligible for study

participation if test results indicate a positive HIV infection. AbbVie will not receive results from the testing and will not be made aware of any positive result.

## TB Screening

Subjects will be tested for TB by either the QuantiFERON-TB Gold Test (or IGRA equivalent) or a TB Skin Test (PPD) at the Screening visit and at Week 52, as specified in the study activity table.

At Screening, all subjects will be assessed for evidence of TB, and if positive, additional risk factors will be evaluated. If a subject had a negative PPD test or QuantiFERON-TB Gold Test (or IGRA equivalent) within 90 days prior to Screening and all protocol-required documentation is available, the test does not need to be repeated, provided nothing has changed in the subject's medical history to warrant a repeat test. Subjects who have tested positive will not have another test performed.

At Week 52, subjects with no prior positive TB test will be tested for TB by either the QuantiFERON-TB Gold Test (or IGRA equivalent) or a TB Skin Test (PPD).

The QuantiFERON®-TB Gold assay test will be supplied and analyzed by the central laboratory. (QuantiFERON-TB test is preferred over TB Skin Test.) Details on the collection, shipment of samples and reporting of results by the central laboratory are provided to investigators in the laboratory manual.

- If the **QuantiFERON-TB Gold Test (or IGRA equivalent) is NOT possible** (or if both the QuantiFERON-TB Gold Test [or IGRA equivalent] and the PPD Skin Test are required per local guidelines), the PPD Skin Test will be performed according to standard clinical practice.
  - The PPD Skin Test should be read by a licensed healthcare professional between 48 and 72 hours after administration. A subject who does not return within 72 hours will need to be rescheduled for another skin test.
  - The reaction will be measured in millimeters (mm) of induration and induration  $\geq 5$  mm is considered a positive reaction. The absence of induration will be recorded as "0 mm," not "negative."
- If subject had a positive QuantiFERON-TB Gold (or IGRA equivalent) or PPD test at Screening, the test should not be repeated. Subjects who have had an ulcerating reaction to the TB Skin Test in the past should not be re-exposed and should not be tested by a PPD skin test.
- If the **TB screening test** (either PPD or the QuantiFERON-TB Gold test [or IGRA equivalent]) is **positive**, or if there is a **repeat indeterminate** QuantiFERON-TB Gold test (or IGRA equivalent) upon retesting, subjects may participate in the study if **further work-up** (according to local practice/guidelines) establishes conclusively that the patient has no evidence of active TB.
- If the subject is diagnosed with **active TB**, the subject should not be randomized in the study and should not receive study drug. Subject will be considered as a **screening failure**.

- If presence of **latent TB** is established, subjects are not required to be treated with prophylactic anti-TB therapy prior to or during the study, if considered low risk for reactivation per investigator judgment.
- If the subject is diagnosed with **active TB** after being randomized, the subject should not receive any further study drug and follow the PD Visit procedure (Section 2.2).
- If **TB (latent or active)** is diagnosed during the study, it is also necessary to report it as an AE in the source documents and eCRFs. In the case of a TB-related AE, a TB supplemental form that provides additional information will be completed by the investigator or designee.

### Hypersensitivity/Anaphylaxis Testing

Anaphylaxis testing is only performed in case of a suspected anaphylactic reaction. Samples should be collected as follows:

Plasma tryptase: Optimally, measurement needs to be obtained from 15 minutes to 3 hours of symptom onset, but no later than 6 hours after (tryptase may remain elevated for 6 or more hours after the onset and therefore may still be informative if obtained after 3 hours); a follow-up tryptase level should be collected a minimum of 2 weeks after any suspected anaphylaxis event.

Plasma histamine: Blood samples for measurement of histamine levels are optimally obtained 5 - 15 minutes after symptom onset and no later than 1 hour.

If a suspected systemic hypersensitivity reaction occurs on site, in addition to tryptase and histamine levels, PK and ADA/nAb samples will also be collected.

In the event that a serious systemic hypersensitivity reaction such as anaphylaxis occurs while the subject is not on site at the study clinic, please advise the treating facility to obtain tryptase and histamine levels to help better understand and characterize the diagnosis.

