Although rare, a potential for hepatic AEs is under constant surveillance by sponsors and regulators. Therefore, this study requires timely detection, evaluation, and follow-up of laboratory alterations in selected liver laboratory parameters to ensure subjects' safety.

Increases in major adverse cardiovascular events (MACE), including myocardial infarction, cerebrovascular accident, and cardiovascular death, reported initially with anti-IL-12/23 agents, such as ustekinumab, have not been observed in longer term studies. While the likelihood of increased MACE is small, all suspected cardiovascular events (serious or nonserious) observed in this study will be adjudicated by an independent committee. An independent Cardiovascular Adjudication Committee (CAC) will adjudicate all observed cardio- and cerebro-vascular events and will remain blinded to treatment allocation (Section 6.3).

Local reactions to subcutaneously-administered biologic therapies are usually limited to redness, swelling, or induration at the injection site. Manifestations of systemic hypersensitivity reactions include anaphylaxis, pruritus, hypotension, and respiratory distress. Both local and systemic hypersensitivity reactions are readily detectable, transient in nature, and manageable with standard medical treatment. Subjects will be closely monitored during study drug administration. An independent Anaphylaxis Adjudication Committee (AAC) will adjudicate observed systemic hypersensitivity and anaphylactic events. The AAC will remain blinded to treatment allocation (Section 6.4).

In conclusion, the benefit-risk profile of risankizumab is considered appropriate for this stage of clinical development. Based on data from the integrated safety analyses, risankizumab is safe and well-tolerated and demonstrates a favorable benefit-risk profile.

For further details, please see findings from completed studies, including safety data, in the risankizumab IB.

In view of the Coronavirus Disease – 2019 (COVID-19) pandemic, the benefit-risk profile of various immunomodulatory therapies on COVID-19 is being evaluated based on real world and clinical trial data. At this time, the effects of risankizumab on the course of COVID-19 are not well defined.

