## 6.4 Anaphylaxis Adjudication Committee

---

While no concerns with systemic hypersensitivity have been identified with the use of risankizumab, the sponsor has established an independent, blinded expert committee to adjudicate events of anaphylaxis based on a pre-specified definition. This independent external AAC will adjudicate observed suspected anaphylactic reactions and will remain blinded to treatment allocation. The events that are adjudicated and the adjudication process will be detailed in the AAC Charter. A supplemental Hypersensitivity Reactions eCRF will be used to collect information pertinent to the events. In addition, the site may be contacted for additional source documentation for relevant events.

If a systemic hypersensitivity reaction such as anaphylaxis is suspected while the subject is not on site, every effort should be made to obtain tryptase and histamine levels from the treating facility to help better understand and characterize the diagnosis. If a suspected systemic hypersensitivity reaction occurs on site, in addition to testing tryptase and histamine levels, PK and ADA/nAb samples will also be collected.

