Coagulation: International Normalized Ratio (INR) c	Enzymes Alanine aminotransferase (ALT) Aspartate aminotransferase (AST) Alkaline Phosphatase (AP) Gamma-glutamyl transferase (GGT/ $\gamma$ -GT) Creatine Kinase (CK) Only if CK is elevated: Troponin (point-of-care) OR Troponin (central lab) + CK-MB	
INFECTION SCREENING		PREGNANCY TESTINGe
Hepatitis B surface antigen (HBs Ag) (qualitative) d Hepatitis B surface antibody (HBs Ab) (qualitative) d Anti-Hepatitis B core (HBc) total (qualitative) d Hepatitis B Virus (HBV) DNA (quantitative) d Anti-Hepatitis C Virus (HCV) (qualitative) d HCV RNA (quantitative) d HIV 1 and HIV-2 Ab (qualitative) d QuantiFERON ® -TB (or Interferon gamma release assay [IGRA] equivalent) and/or purified protein derivative (PPD)		Urine Pregnancy test (local) f Serum Pregnancy test g
		PK/IMMUNOGENICITY
	ADDITIONAL TESTING	Serum risankizumab concentration Serum ADA Serum nAb
	IgE	ANAPHYLAXIS TESTINGh
		Serum risankizumab concentration i ADA i nAb i Tryptase j Histamine

- Performed only at Baseline visit (following a minimum 8-hour fast).
- FSH testing is to be done at Screening in all women aged  $\leq 55$  years with no menses for 12 or more months without an alternative medical cause.
- INR test only performed if ALT or AST  $> 3 \times$  ULN (upper limit of normal).
- Performed only at Screening.
- Pregnancy testing is not required for female subjects of non-childbearing potential (defined in protocol).
- Urine pregnancy test will be performed at every dosing visit and the Week 52/PD Visit and must be conducted prior to study drug dosing. Negative urine pregnancy test results must be confirmed prior to study drug dosing.
- Serum pregnancy test is conducted at Screening and at other visits only if urine pregnancy test is positive. Negative serum pregnancy test results must be confirmed prior to study drug dosing.
- Only performed in case of a suspected anaphylactic reaction.
- PK and ADA/nAb samples drawn in context of a suspected anaphylactic reaction are collected in addition to those collected at scheduled time points for PK/immunogenicity and are only collected if a suspected anaphylactic reaction occurs while at the study site.

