## APPENDIX O. CLINICAL CRITERIA FOR DIAGNOSING ANAPHYLAXIS

**Anaphylaxis** is highly likely when any one of the following 3 criteria is fulfilled:

- 1) Acute onset of an illness (minutes to several hours) with involvement of the skin, mucosal tissue, or both (e.g., generalized hives, pruritus or flushing, swollen lips-tongue-uvula)

AND AT LEAST ONE OF THE FOLLOWING

- a) Respiratory compromise (e.g., dyspnea, wheeze-bronchospasm, stridor, reduced peak expiratory flow [PEF], hypoxemia)
  - b) Reduced BP or associated symptoms of end-organ dysfunction (e.g., hypotonia [collapse], syncope, incontinence)
- 2) Two or more of the following that occur rapidly after exposure to a likely allergen for that subject (minutes to several hours):
    - a) Involvement of the skin-mucosal tissue (e.g., generalized hives, itch-flush, swollen lips-tongue-uvula)
    - b) Respiratory compromise (e.g., dyspnea, wheeze-bronchospasm, stridor, reduced PEF, hypoxemia)
    - c) Reduced BP or associated symptoms (e.g., hypotonia [collapse], syncope, incontinence)
    - d) Persistent gastrointestinal symptoms (e.g., crampy abdominal pain, vomiting)
  - 3) Reduced BP after exposure to known allergen for that subject (minutes to several hours):
    - a) Infants and children: low systolic BP (age specific) or greater than 30% decrease in systolic BP\*
    - b) Adults: systolic BP of less than 90 mm Hg or greater than 30% decrease from that person's baseline.

\* Low systolic BP for children is defined as less than 70 mm Hg from 1 month to 1 year, less than (70 mm Hg + [2 × age]) from 1 to 10 years, and less than 90 mg Hg from 11 to 17 years.

**Serious Systemic Hypersensitivity Reaction:** A hypersensitivity reaction is a clinical sign or symptom, or constellation of signs or symptoms, caused by an inappropriate and excessive immunologic reaction to study drug administration. A systemic hypersensitivity reaction is a hypersensitivity reaction that does not occur at the local site of study drug administration (e.g., not an injection site reaction). A serious systemic hypersensitivity reaction is a systemic hypersensitivity reaction that fulfills criteria for a SAE.

In the event of an anaphylactic reaction, blood samples will be drawn per Section 3.12 after the onset of the reaction. Separate instructions for the collection, handling, storage, and shipping of these labs will be provided outside of the study protocol.

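### The Protocol and Operations Manual set two different triggers for tryptase, histamine, PK and ADA/nAb sampling after a reaction, so a non-anaphylactic systemic reaction may go unsampled

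*Protocol*

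**What the plan says.** **Sampling tied to anaphylaxis.** The testing text in Operations Manual 3.12 (Hypersensitivity/Anaphylaxis Testing) begins "Anaphylaxis testing is only performed in case of a suspected anaphylactic reaction". In the laboratory table of the same section, the footnote to the anaphylaxis panel reads "Only performed in case of a suspected anaphylactic reaction". The footnote on PK and ADA/nAb says that these samples "are only collected if a suspected anaphylactic reaction occurs while at the study site". Operations Manual 3.11 and the closing paragraph of Appendix O also call for blood samples in the event of (suspected) anaphylaxis, though without an exclusive word.

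**Sampling tied to systemic hypersensitivity.** Later in the same 3.12 testing text: "If a suspected systemic hypersensitivity reaction occurs on site, in addition to tryptase and histamine levels, PK and ADA/nAb samples will also be collected". Protocol 6.4 has the same rule, beginning "If a suspected systemic hypersensitivity reaction occurs on site, in addition to testing tryptase and histamine levels" and going on to PK and ADA/nAb.

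**Definitions.** Appendix O gives anaphylaxis a three-criterion clinical definition and defines the wider class separately: "A systemic hypersensitivity reaction is a hypersensitivity reaction that does not occur at the local site of study drug administration".

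**Committee scope.** Protocol 2.2 says that the Anaphylaxis Adjudication Committee "will adjudicate observed systemic hypersensitivity and anaphylactic events". Protocol 6.4 says that it "will adjudicate observed suspected anaphylactic reactions", and leaves the list of adjudicated events to the committee's charter.

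**The concern.** A site needs one rule for when to draw these samples, and must apply it within minutes. The documents give two, and the same section of the Operations Manual contains both. For a systemic reaction that is not suspected to be anaphylaxis, one rule requires the samples and the other rules them out.

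At stake are the mediator levels and the drug and antibody measurements taken at the time of the reaction. These would help to characterise it and relate it to exposure and immunogenicity. If sites resolve the conflict differently, those data will also be incomplete in a way that depends on site and not on the event.

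**Working it through.** This is a comparison of texts; the plan gives no figure to reproduce.

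**Step 1. The triggers side by side.**

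| Place | Event that triggers sampling | Rules out other events? |
|---|---|---|
| Ops Manual 3.12, opening of testing text | Suspected anaphylaxis | Yes |
| Ops Manual 3.12, footnote to anaphylaxis panel | Suspected anaphylaxis | Yes |
| Ops Manual 3.12, footnote on PK and ADA/nAb | Suspected anaphylaxis on site | Yes |
| Ops Manual 3.11 | Suspected anaphylaxis | No |
| Ops Manual Appendix O, closing paragraph | Anaphylaxis | No |
| Ops Manual 3.12, later paragraph of testing text | Any suspected systemic hypersensitivity reaction on site | – |
| Protocol 6.4 | Any suspected systemic hypersensitivity reaction on site | – |
| Ops Manual 3.12, off site | *Serious* systemic reaction such as anaphylaxis | – |
| Protocol 6.4, off site | Suspected systemic reaction such as anaphylaxis, no *serious* qualifier | – |

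The first three rows contradict the two broad on-site rows outright. Section 3.11 and Appendix O are narrower in wording but do not exclude the wider class. The two off-site rows differ from each other.

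**Step 2. Are the two terms interchangeable?** No. Take generalised hives on site after a dose, with no other sign, judged a reaction to study drug. Appendix O criterion 1 needs skin or mucosal involvement plus respiratory compromise or reduced blood pressure (or end-organ symptoms). Criterion 2 needs at least two listed features. Criterion 3 needs reduced blood pressure. Hives alone meet none of these, yet the reaction is away from the injection site and so is systemic hypersensitivity. Protocol 6.4 also names anaphylaxis as an example of a systemic reaction, not as its equivalent.

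**Step 3. Apply both rules.** Protocol 6.4 and the later paragraph of 3.12 say to draw tryptase, histamine, PK and ADA/nAb. The opening line of 3.12 and both footnotes say not to, unless the site suspects anaphylaxis anyway.

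**Step 4. Can the samples be obtained later?** Under 3.12, histamine is to be drawn no later than 1 hour after onset and tryptase no later than 6 hours. A query to the sponsor could easily outlast the first limit.

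**Step 5. Do scheduled samples fill the gap?** In part. The visit lists in Operations Manual 2.1 and 2.2 schedule ADA/nAb at Baseline, Weeks 4 and 16, and Week 52/PD. Section 3.13 puts dosing-visit samples within 60 minutes before the dose. A reaction at Baseline, Week 4 or Week 16 therefore has at least a same-day pre-dose ADA/nAb sample. The Week 28 and Week 40 lists contain neither PK nor ADA/nAb. At those visits the event-driven sample is the only one specified.

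**Step 6. How many planned doses does this cover?** Planned randomization is 62 + 62 = 124 to risankizumab and 31 to placebo, with five dosing visits each.

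- All doses: 155 × 5 = 775.
- Risankizumab doses: 124 × 5 + 31 × 3 = 620 + 93 = 713.
- Doses at Weeks 28 and 40, all risankizumab: 155 × 2 = 310, which is 310 / 775 = 40% of planned doses.

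These are upper limits on occasions, not counts of reactions. They assume no discontinuation and ignore the at-home dosing that the COVID-19 provisions allow.

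**The case against.** The case for treating this as a minor wording slip has several parts.

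- **The broad trigger is visible where sites work.** Every dosing-visit list has an item for hypersensitivity testing if applicable, and the 3.12 heading names both hypersensitivity and anaphylaxis. This is fair, but the lists do not say when testing applies, and the text under that heading opens with the restriction.
- **The event is not lost.** This stands. It is recorded as an AE, Protocol Table 2 and Operations Manual 3.11 call for the supplemental hypersensitivity form, and SAP Appendix B has a separate hypersensitivity search with serious events in the AE overview.
- **PK and ADA data exist anyway.** This stands for Baseline, Week 4 and Week 16, at least for pre-dose ADA/nAb. It does not stand for Weeks 28 and 40.
- **Committee scope is for the charter.** This largely stands. Protocol 2.2 is background text that points to 6.4. The data monitoring section (Protocol 6.2) and SAP Appendix B speak only of adjudicated anaphylaxis, in line with 6.4. The charter is not among the documents and may settle the matter.

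A reader might infer that the adjudicated anaphylaxis count in the SAP must be too low. The documents do not support that. A reaction that meets no Appendix O criterion is not anaphylaxis under them, so leaving it out does not lower the count. Those criteria are clinical and do not use tryptase or histamine. An undercount would need true anaphylaxis that the site did not suspect, and neither trigger wording creates that. A reader might also infer that the site's label decides what the committee sees. No text says so, and the sponsor receives the supplemental form for the wider class of reactions.

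**Conclusion.** The contradiction in the sampling trigger is real and is in current text. Its effect is limited to event-driven samples: under the restrictive wording, a non-anaphylactic systemic reaction would go without tryptase, histamine, PK and ADA/nAb samples that Protocol 6.4 requires on site. The loss is permanent for the time-limited samples. It is most complete at Weeks 28 and 40, up to 310 planned doses, where no scheduled drug or antibody sample exists.

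How many events this would touch cannot be estimated, because the documents give no reaction rate. The conclusion rests on the Appendix O definitions applying throughout and on some sites following the restrictive wording. No statement that the Protocol overrides the Operations Manual, or the reverse, was found; the manual is the Protocol's Appendix F.

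The difference in committee scope between Protocol 2.2 and 6.4 is a separate wording inconsistency. Such a reaction may or may not be adjudicated, depending on the charter. No primary or key secondary efficacy endpoint is affected. The point is more than clerical because it changes which samples are drawn, but it is modest.

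**What to change.** 1. Reconcile Operations Manual 3.11, 3.12 (the opening line of the testing text, its later paragraphs and both laboratory-table footnotes) and Appendix O with Protocol 6.4, so that one on-site trigger applies everywhere and uses the Appendix O terms.
2. Do the same for the off-site request to the treating facility, and settle whether the *serious* qualifier applies.
3. Refer to the agreed trigger wherever the visit lists mention hypersensitivity testing.
4. Separately, align the description of the committee's remit in Protocol 2.2 with 6.4 and with the charter. The documents do not settle which scope is intended, so that choice is left to the sponsor.

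The cost is wording changes in the Protocol and Operations Manual, a check against the charter and, if the broader trigger is kept, possibly a few extra blood samples. Treatment of the reaction is not touched.

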### COVID-19 Pandemic-Related Acceptable Protocol Modifications

If travel restrictions or other changes in local regulations in light of the COVID-19 pandemic prevent the subject from having blood drawn for laboratory testing at the study site, if possible, arrange for subjects to have laboratory work done at a local lab, hospital, or other facility. Local lab results should be obtained along with reference ranges. Local lab results and reference ranges need to be entered into the EDC system and also kept with the subjects' source documentation. Local lab results should be reviewed by the investigator as soon as possible.

If laboratory samples cannot be obtained, study drug administration may be continued provided the investigator has reviewed all prior laboratory results and confirms and discusses with the subject that there is no safety concern for the subject to continue use of the study drug in the absence of current labs. The subject should be scheduled for laboratory draws as soon as feasible.

